10.2 Recording adverse events

All adverse events will be recorded in the medical records in the first instance. All adverse events will be recorded from consent to the end of trial.

All adverse events will be recorded with clinical symptoms and accompanied with a simple, brief description of the event, including dates as appropriate.

Non-serious Adverse Events (AEs) and Serious Adverse Events (SAEs) associated with COVID-19 infection will not be collected in the CRFs or reported to Sponsor for this trial. Refer to ‘Serious Adverse Events which do not require immediate reporting’ section for further details.

10.3 Assessments of Adverse Events

Each adverse event will be assessed for severity, causality, seriousness and expectedness as described below.

10.3.1 Severity

Category	Definition
Mild	The adverse event does not interfere with the participant's daily routine, and does not require intervention; it causes slight discomfort
Moderate	The adverse event interferes with some aspects of the participant's routine, or requires intervention, but is not damaging to health; it causes moderate discomfort
Severe	The adverse event results in alteration, discomfort or disability which is clearly damaging to health

10.3.2 Causality

The assessment of relationship of adverse events to the administration of IMP is a clinical decision based on all available information at the time of the completion of the case report form.

The causality assessments will be captured in the trial specific CRF, SAE Log or SAE Reporting Form.

The following categories will be used to define the causality of the adverse event:

Category	Definition
Related	A causal relationship between an IMP/investigational treatment and an adverse event is at least a reasonable possibility , i.e., the relationship cannot be ruled out.
Not related	There is no reasonable possibility of a causal relationship between an IMP/investigational treatment and an adverse event.

10.3.3 Expectedness

Category	Definition
Expected	An adverse event which is consistent with the information about the IMP listed in the current approved Reference Safety Information (RSI) for the trial.

Unexpected	An adverse event which is not consistent with the information about the IMP listed in the current approved Reference Safety Information (RSI) for the trial.
-------------------	---

* this includes listed events that are more frequently reported or more severe than previously reported

The RSI to be used to assess expectedness is section 4.8 of the SmPC for octaplasLG (human plasma proteins).

10.3.4 Seriousness

All events are assessed for seriousness as defined for an SAE in section 10.1.

10.4 Procedures for recording and reporting Serious Adverse Events

All serious adverse events (SAEs/SARs/SUSARs) will be recorded in the medical records in the first instance. Serious Adverse Events (SAEs) related to COVID-19 will not be collected in the CRFs or reported to Sponsor for this trial. Refer to ‘Serious Adverse Events which do not require immediate reporting’ section for further details.

All other SAEs will be recorded in the CRF, the Sponsor’s SAE Recording Log and SAE Reporting Form.

All SAEs will be recorded from randomisation until the end of the trial (i.e. 28 days after enrolment).

[figure not shown]
All SAEs (except COVID-19 related SAEs) must be recorded on a SAE Reporting Form. The CI/PI or designated individual will complete the sponsor’s SAE form email to the Sponsor at [contact], within 24 h of his / her becoming aware of the event. The Chief or Principal Investigator will respond to any SAE queries raised by the sponsor as soon as possible.

**Completed SAE forms must be sent within 24 hours of becoming aware of the event to the Sponsor
Email forms to [contact]**

Managing serious adverse events in a multi-site trial

- SAEs from all sites must be reported to Sponsor as detailed above. The SAE Reporting Forms should be emailed to the CI at the same time as forwarding to the Sponsor. The CI will perform an assessment of the SAE in collaboration with the Sponsor. It should be noted that the CI cannot overrule the causality assessment provided by the PI.
- SAE Recording Logs should be sent to UCLH data manager as per the data management plan, and to the Sponsor upon request.

Flow Chart for SAE Reporting

10.5 Serious Adverse Events which do not require immediate reporting

SAEs associated with COVID-19 disease do not require recording in the CRF, SAE Recording Log or SAE Reporting Form. However, if the relationship between the IMP and an SAE cannot be ruled out the SAE must be recorded and reported to Sponsor as detailed above.

There is high rate of expected deterioration in this group of patients. Anticipated adverse events/interventions associated with COVID-19 infection which are not required to be captured as an SAE/AE include:

- abnormal pathology results from presentation (including inflammatory markers related to a hyperinflammatory response)
- secondary infection
- renal failure
- cardiac disease e.g. arrhythmias, right heart failure
- intubation and ventilation
- VTE/arterial thrombosis
- end organ damage developing either biochemical e.g. AKI, liver impairment or clinical e.g. Intubation, thrombosis (either venous or arterial such as stroke)
- death from COVID19

This will be captured within the medical notes. These represent SAEs but are anticipated based on the natural history of the COVID-19 disease and so do not require immediate reporting. Mortality will be captured as an endpoint.

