- B. Citrate reactions: Some patients treated with PEX present with features of hypocalcaemia (fatigue, paraesthesia, tremor, and hypocalcemia). This is treated with calcium boluses, but offset by a calcium infusion throughout PEX.
- C. Risk of viral transmission: Standard measures to prevent infections resulting from the use of medical products prepared from human blood or plasma include selection of donors, screening of individual donations and plasma pool for specific markers of infection and the inclusion of effective manufacturing steps for the inactivation/removal of viruses. When medicinal products prepared from human blood or plasma are administered, the possibility of transmitting infective agents cannot be totally excluded. However Octaplas LG undergoes a number of additional pathogen inactivation steps and is considered very safe.

The table below summarises the risks, frequencies and mitigations of the IMP(s) and NIMP(s) (delete NIMP if it is not applicable)

Name of IMP(s) / NIMP	Potential risk	Risk Frequency	Risk Management
Octaplas	-Reactions to plasma - -Pathogen transmission	-Severe reactions- grade 4- anaphylaxis <1% -Due to nanofiltration and S/D processing, this is the safest and most effective plasma available	-Any reactions treated with antihistamine, paracetamol and /or hydrocortisone -PEX would be stopped if any severe reaction/anaphylaxis -routine viruses are checked pre PEX.
PEX procedure	Citrate toxicity	10-20% of procedures	IV calcium is run during PEX and added boluses given if required

Vascath insertion	Infection, bleeding, thrombosis	Approx. 10%	Lines are changed weekly to reduce infection, intermediate LMWH given, reducing thrombosis. Bleeding rare as lines inserted by USS
-------------------	---------------------------------	-------------	--

Type A = No higher than the risk of standard medical care

5 Objectives

The rationale of this study is to compare outcomes of patients receiving PEX to those who do not. We hope to ascertain if PEX provides a clinical benefit to expand its use nationally and internationally, as there is currently no treatment which improves the morbidity and mortality of patients with severe COVID-19.

Primary objectives:

To compare reduction in inflammatory markers between Plasma Exchange (PEX) and control groups in patients with severe COVID

Secondary objectives:

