12.1.2 Secondary outcomes

1. Number of patients requiring mechanical ventilation who required only supplemental O₂/CPAP at study entry. This will be captured throughout the period of the study, by review of the oxygen requirements and ventilatory support required throughout the study (O₂ requirement or PaO₂:FiO₂ (P:F ratio) sequentially)
2. 50% decrease in VWFAg/ADAMTS 13 activity ratio from baseline to end of PEX.
3. Prevent deterioration in myocardial function on ECHO/ cardiac parameters -monitoring of cardiac function through echocardiogram and/ or BNP and Troponin levels throughout study period
4. Clinical thrombotic events documented by imaging either venous DVT/PE, or arterial thrombus (cardiac, neurological and peripheral vascular) throughout the study period
5. Incidence of acute kidney injury as defined by KDIGO criteria throughout study period
6. Mortality at 28 days

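### The COVID-19 event exemption in Sections 10.2, 10.4 and 10.5 is not reconciled with the scheduled outcomes, and can leave an ambiguous line- or procedure-related infection or thrombosis uncounted

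*Combined protocol and SAP*

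**What the plan says.** Section 10.5 is headed as an exemption from immediate reporting, but its rule goes further: "SAEs associated with COVID-19 disease do not require recording in the CRF, SAE Recording Log or SAE Reporting Form". It then introduces a list with "Anticipated adverse events/interventions associated with COVID-19 infection which are not required to be captured as an SAE/AE include". The list names secondary infection, renal failure and AKI, intubation, venous and arterial thrombosis, and death from COVID-19. Of these events it says: "This will be captured within the medical notes". Section 10.2 applies the same rule to non-serious events: "Non-serious Adverse Events (AEs) and Serious Adverse Events (SAEs) associated with COVID-19 infection will not be collected in the CRFs". Section 10.4 repeats it for SAEs.

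Two provisions limit the exemption. Section 10.5 adds that "if the relationship between the IMP and an SAE cannot be ruled out the SAE must be recorded" and reported. Section 10.4 sends every SAE that is not COVID-19-related to the CRF, the SAE log and the SAE form.

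Section 12.1.2 lists mechanical ventilation, imaging-documented thrombosis and AKI among the secondary outcomes, the last as "Incidence of acute kidney injury as defined by KDIGO criteria throughout study period". Section 9.4.1 schedules thrombotic events, deterioration to ventilation, antibiotic need and daily renal bloods for both Days 1-5 and Days 6-28. Complications of the vascath are listed for Days 1-5 only, which also apply to a repeat block.

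The risk table in Section 4 gives the vascath hazards as "Infection, bleeding, thrombosis", at a frequency of about 10%.

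**The concern.** The same clinical event can fall under two instructions. A DVT is something to collect under 9.4.1 and an outcome under 12.1.2, but if it is attributed to COVID-19 it is also something that 10.2 and 10.4 say the CRF will not hold. The authors resolved this for death, which Section 10.6 places on the CRF. No equivalent sentence exists for thrombosis, AKI or ventilation.

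Attribution then decides what is counted as harm. The trial is unblinded (Section 6.1), and the PEX vascath belongs to the PEX arm; Section 4 says that the other central lines such patients may have are not suitable for PEX. Infection and thrombosis are hazards of that line and also common in the disease, so a single event will often be hard to assign. If it is assigned to COVID-19 it stays out of the SAE log. The only oversight group described, the TMG in Section 14.1, reviews SAEs and can recommend stopping (Section 9.9), so it may not see the event.

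**Working it through.** **Step 1: set the sections side by side.**

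| Event | Exempt in 10.5 | Outcome in 12.1.2 | 9.4.1, Days 1-5 | 9.4.1, Days 6-28 | Vascath hazard, Section 4 |
|---|---|---|---|---|---|
| Venous/arterial thrombosis | Yes | Yes | Listed | Listed | Yes |
| Intubation/ventilation | Yes | Yes | Listed | Listed | No |
| Renal failure/AKI | Yes | Yes | Daily renal bloods | Daily renal bloods | No |
| Secondary infection | Yes | No | Antibiotic need only | Antibiotic need only | Yes |
| Bleeding | No | No | As a vascath complication | No specific item | Yes |
| Vascath complication | Not named | No | Listed | Not listed | – |

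The three outcomes have a data source outside the adverse event forms. AKI can be derived from creatinine (Section 9.5), and Appendix 3 lists changes in respiratory support and haemofiltration. Infection has no direct item in either period. Vascath complications drop out after Day 5 unless PEX is repeated, although Section 4 describes weekly line changes and no section says that the line is out by Day 5. General adverse event collection continues to Day 28, but that is the route which 10.2 closes for events attributed to COVID-19. Appendix 3 has no row for thrombosis, infection or vascath complications.

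**Step 2: follow one event.** Take an infection on Day 8 in a PEX patient.

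- Recognised as line-caused and serious: reportable under 10.4, with no need of the override.
- Judged to be COVID-19-related: exempt under 10.2, 10.4 and 10.5 unless the override applies. The override refers to the IMP, which Section 7.1 defines as OctaplasLG. It also covers SAEs only, so a non-serious event has no override at all.
- What remains in the trial data is an antibiotic record.

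A line thrombosis on Day 8 fares better: it is still a scheduled thrombotic event, although not identified as a line complication.

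**Step 3: scale.** The plan states no figure for lost events, so there is none to reproduce. Inputs: 20 to 40 patients at 1:1 (Sections 6.1 and 12.2.1), hence 10 to 20 on PEX; vascath frequency about 0.10 (Section 4).

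- Expected complications of any type: 10 × 0.10 = 1 and 20 × 0.10 = 2.
- Chance that at least one occurs: 1 − 0.9^10 = 0.651 and 1 − 0.9^20 = 0.878.
- If the rate were 5% to 20% (assumed range): 0.5 to 2 in 10 patients and 1 to 4 in 20.

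Expected loss is n × 0.10 × q, where q is the fraction of complications that are exempt in type, attributed to COVID-19 and missed by 9.4.1. The documents give no value for q. Over its whole range, 0 to 1, the loss is 0 to 1 event with 10 PEX patients and 0 to 2 with 20. Because bleeding is not exempt and Day 1-5 complications are scheduled items, q should be below 1.

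**Step 4: background.** Section 3 gives 17% to 31% thromboembolism in critically ill COVID-19 patients despite prophylaxis. Per arm that is 1.7 to 3.1 events in 10 patients (10 × 0.17; 10 × 0.31) and 3.4 to 6.2 in 20. The trial population may be less ill. Even so, one extra line thrombosis could easily be taken for disease.

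**The case against.** The best defence is that the protocol runs two tracks: outcomes are collected as outcomes, and the exemption only stops them being entered again as adverse events. Death is the model, being exempt in 10.5 and on the CRF in 10.6. On this view 9.4.1 and 10.5 are compatible, and since the CRF is not among the documents, nobody can say that a field is missing. This largely stands for ventilation, thrombosis and AKI. A reader might infer that 10.5 removes these outcomes from the trial data; the scheduled items in 9.4.1 and the renal bloods do not support that.

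Second, the override may be wider than it looks. Section 10.3.2 defines a related event by reference to the IMP or investigational treatment, the adverse event definition in 10.1 includes procedural interventions, and Section 9.3 describes the IMP as given by plasmapheresis. This stands as far as showing ambiguity. Section 10.5 itself, and the opening sentence of 10.3.2, name the IMP alone.

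Third, a reader might infer that any error runs one way. Section 4 says that patients with severe COVID-19 are likely to need central access, so SOC patients also carry some line risk, and exempt events will occur in both arms. What is specific to the PEX arm is the additional vascath, so an imbalance is possible but its direction and size are not established.

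**Conclusion.** The point holds in a limited form. Sections 10.2, 10.4 and 10.5 conflict on their face with 9.4.1 and 12.1.2 about what reaches the CRF, and only death is explicitly resolved. The practical exposure is an ambiguous line- or procedure-related event, chiefly infection and to a lesser degree thrombosis, that unblinded staff attribute to COVID-19, mainly after Day 5. Such an event can be absent from the CRF as a harm, from the SAE log and from TMG review.

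The scale is at most about 1 to 2 events in the PEX arm. This rests on the protocol's approximate 10%, which pools infection, bleeding and thrombosis at any severity, and on reading it as a per-patient risk. The figures of 65% and 88% might be read as the chance of losing an event. They are the chance that any vascath complication occurs, and the documents give no basis for a misattribution rate. With counts this small, however, one or two misassigned events could make up most of the line-related signal, so the recording rule is worth tightening.

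**What to change.** - Limit the exemption in 10.5 to expedited reporting, which is what its heading describes.
- Amend 10.2, 10.4 and 10.5 to agree with 9.4.1 and 12.1.2: all secondary-outcome events, all infections, and all complications of the vascath or the PEX procedure are recorded on the CRF to Day 28 in both arms, whatever the attributed cause.
- Add vascath complications and an infection item to the Day 6-28 list in 9.4.1, with matching rows in Appendix 3.
- Extend the override from the IMP to *the IMP, the PEX procedure or the vascath*, and use the same phrase in 10.3.2.
- Tabulate these events by arm, with attribution as a separate column so that it describes an event but does not decide whether it is counted.

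The cost is wording in a few sections, a few CRF fields and a small amount of extra data entry. Most of the information is already in the medical notes or scheduled. Treatment, sample size and the primary analysis are unaffected.

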10.6 Notification of Deaths

Deaths related to COVID-19 disease is an endpoint of the trial and will be captured in the CRF. All other SAEs should be reported to Sponsor as described in the Procedures for recording and reporting Serious Adverse Events section above.

10.7 Reporting SUSARs

The sponsor will notify the main REC and MHRA of all SUSARs. SUSARs that are fatal or life-threatening must be notified to the MHRA and REC within 7 days after the sponsor has learned

of them. Other SUSARs must be reported to the REC and MHRA within 15 days after the sponsor has learned of them.

10.8 Development Safety Update Reports

The sponsor will provide the main REC and the MHRA with Development Safety Update Reports (DSUR) which will be written in conjunction with the trial team and the Sponsor's office. The report will be submitted within 60 days of the Developmental International Birth Date (DIBD) of the trial each year until the trial is declared ended.

10.9 Pregnancy

Pregnancy is considered to be highly unlikely during the study as participants are hospitalised for the duration of the trial.

In the unlikely event that a female participant or the female partner of a male participant becomes pregnant at any point during the trial, a completed trial specific Pregnancy Reporting Form will be emailed to the Sponsor [contact], within 24 hours of his / her becoming aware of the event in line with the Sponsors SOP (JRO/INV/S05). The Chief or Principal Investigator will respond to any queries raised by the sponsor as soon as possible.

**Completed Pregnancy Reporting Forms must be sent within 24
hours of becoming aware of the event to the Sponsor
Email forms to [contact]**

The Sponsor must be kept informed of any new developments involving the pregnancy through the completion of a follow-up Pregnancy Reporting Form. Any pregnancy that occurs in a female trial subject during a clinical trial should be followed to termination or to term.

Consent to report information regarding the pregnancy must be obtained from the pregnant participant. A trial-specific pregnancy monitoring information sheet and informed consent form for trial participants and the partners of trial participants must be used for this purpose.

With consent additional information regarding the pregnancy will be collected and reported to the Sponsor, the Sponsor will advise on the length of follow up of the pregnancy/ child on a case by case basis,

10.10 Reporting Urgent Safety Measures and other safety events

If any urgent safety measures are taken the CI/ PI shall immediately and in any event no later than 3 days from the date the measures are taken, give written notice to the MHRA, the relevant REC and Sponsor of the measures taken and the circumstances giving rise to those measures.

10.11 Notification of Serious Breaches to GCP and/or the protocol (SPON/S15)

A “serious breach” is a breach which is likely to effect to a significant degree –

- (a) the safety or physical or mental integrity of the participants of the trial; or
- (b) the scientific value of the trial.

The sponsor of a clinical trial shall notify the licensing authority in writing of any serious breach of –

(a) the conditions and principles of GCP in connection with that trial; or (b) the protocol relating to that trial, as amended from time to time, within 7 days of becoming aware of that breach.

The sponsor will be notified immediately of any case where the above definition applies during the trial conduct phase. The sponsor’s SOP on the ‘Notification of violations, urgent safety measures and serious breaches’ will be followed.

10.12 Reporting incidents involving a medical device(s)

Any adverse incident involving a medical device should be reported to the manufacturer of the device.

This is especially important where the incident has led to or, was it to occur again could lead to an event classified as serious (see section 9.2 for definition of SAE). Other minor safety or quality problems should be reported along with incidents that appear to be caused by human error.

Local trust reporting procedures may also need to be followed. It is the responsibility of the PI and trial site team to ensure they are aware of any specific local requirements for reporting device incidents.

Sites to report to the manufacturer and an incident form forwarded to the central trial coordinator.

Adverse incidents related to a medical device can be reported directly to the MHRA via the online system (www.mhra.gov.uk). Alternative contact details: Medicines & Healthcare products Regulatory Agency Adverse Incident Centre ([contact]; [contact]).

11 Data management and quality assurance

11.1 Confidentiality

All data will be handled in accordance with the UK Data Protection Act 1998.

Case Report Forms (CRFs) for sites will not bear the participant's name or other personal identifiable data. The participant's initials, date of birth and trial identification number, will be used for identification and this will be clearly explained to the patient in the Patient information sheet. Patient consent for this will be sought.

11.2 Data collection tools and source document identification

At UCLH, All data will be available on hospital IT clinical system (EPIC) as source documentation and captured on Sealedenvelopes.com. As there may be a number of datapoints re observations in a 24 hour period, only those captured within the daily trial update, eg as a median will be recorded.

Data will be collected from sites on Trial specific case report forms (CRFs)

Source data are contained in source documents and must be accurately transcribed on to the CRF. Examples of source documents are medical records which include laboratory and other clinical reports etc.

A source document list will be implemented prior to the start of the trial to identify:

which data is to be recorded directly onto the CRF;

which data is recorded firstly into source documents, such as medical notes, and then transcribed into the CRF

It is the responsibility of the investigator to ensure the accuracy of all data entered in the CRFs. The delegation log will identify all those personnel with responsibilities for data collection and handling, including those who have access to the trial database.

